	
 • Opioid-related side effects (e.g., nausea and vomiting, constipation, urinary retention, pruritis, drowsiness, respiratory depression) 
Functional outcomes
 
■ Range of motion (ROM) ([REDACTED]
 
 ○ Number of days to achieve key milestones in affected knee (e.g., 90 degree flexion) ○ Pain scores before, during, and after ROM testing 
 • Timed Up and Go (TUG) test • 6 minute walk test (6MWT) • Fixed distance walk test 
Surveys
 
 • Change in pain, physical function, and stiffness as measured by the Western Ontario McMaster University Osteoarthritis Index (WOMAC) • Pain interference with activities of daily living as recorded on numerical rating scale (BPI-9) • Patient Global Impression of Change (PGIC) • Pain Catastrophizing Scale (PCS) • Time to meet recovery milestones (e.g., discharge date) • Subject satisfaction with the study and therapy as measured by a Subject Satisfaction Survey
Exploratory Measurements	
 • Analyses of primary and secondary endpoints at study intervals not specified in Section 3.0 • Subject-shaded diagrams of pain and paresthesia • Clinician Satisfaction Survey
Key Demographic Information	
 • Body Mass Index (BMI) ■ Surgical approach [REDACTED] • Use of post-operative drains • Type of knee implant used (i.e., manufacturer and model)

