3.3 Secondary Outcomes

Secondary outcome measures will provide additional information on pain and function, which will be used to aid in the design of future clinical studies.

Brief Pain Inventory-Short Form (BPI)

The BPI is a widely used assessment designed to measure pain intensity and the interference of pain on daily activities and moods (Cleeland and Ryan 1994). The BPI is recommended by the Initiative on Methods, Measurement, and Pain Assessment in Clinical Trials (IMMPACT) panel and has demonstrated validity and reliability across many cultures and languages (Cleeland and

Ryan 1994; Tan et al. 2004; Dworkin et al. 2005). The IMMPACT panel was assembled to develop consensus recommendations to improve and standardize the design and conduct of clinical trials involving treatments for pain.

Cumulative Analgesic usage

The amount and type of analgesic used by the subject will be recorded daily in a diary before TKA surgery, from the subject's records during their hospital stay, in daily diaries after discharge from the hospital, and at each visit following End of Treatment. Specific analgesic information that will be collected may include Patient Controlled Analgesia (PCA) dosage requests, PCA dosage, intravenous (IV) medications (opioids and non-opioids), oral opioids, and oral non-opioid pain medications. This information will provide an indirect measure of pain intensity, as usage of analgesics may relate to the amount of pain experienced. Narcotic usage may be converted into a morphine equivalent dosage (MED). The use of other methods of pain relief will also be recorded (e.g., cryotherapy).

Opioid Related Side Effects

Opioid pain medications are associated with a wide variety of side effects. Common side effects include nausea and vomiting, constipation, urinary retention, pruritis, drowsiness, and respiratory depression. Subjects may be questioned for each of these side effects throughout the study. Side effects from narcotic therapy will be collected but not reported as adverse events.

Range of motion

Adequate knee ROM is essential for activities of daily living but is limited by postoperative pain.. The active ROM (AROM; no assistance from clinical staff) and passive ROM (PROM; assisted by clinical staff) will be assessed during the study, and when possible the same clinical staff members at each site should take all ROM measurements to limit intertester variability.

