Discharge criteria differ between hospitals, but may include the following: 1) patient is medically stable, 2) pain controlled without nerve block (*i.e.*, single shot or continuous regional/neuraxial nerve blocks), 3) patient able to walk 30 meters ensuring Activities of Daily Living can be completed at home, and 4) patient can walk a set number of stairs (e.g., half a flight). The time until the subject meets criteria related to hospital discharge will be measured. Also, the subject’s length of stay in the hospital following TKA will be recorded (number of days and/or hours), as well as discharge destination (*e.g.*, home, acute inpatient rehabilitation, skilled nursing facility). In

addition, the time required to reach other important recovery milestones may be measured, such as 1) walking with assistive device (e.g., cane, quad stick, walker), 2) walking without assistive device, 3) return to work, and 4) cessation of narcotic usage.

Subject satisfaction survey

A survey will be administered to the subjects at study intervals to assess their satisfaction with the study and postsurgical pain therapies.

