6.5.8 Follow-up Visits: Visits 12-(2 months), Visit 13 (3months)

Visits will occur at 2 months (Visit 12) and 3 months (Visit 13) after TKA surgery. The 2-month visit may be completed via telephone and the 3-month visit will occur in person. At each visit, subjects will be queried for AEs.

The following outcome measures may be assessed during the Visit 12 telephone call:

- BPI-5 ([REDACTED])
- BPI-9 [REDACTED]
- PGIC
- Time to recovery milestones
- Current pain treatments/analgesic usage
- Assess for opioid-related side effects

In addition to the above, the following may be assessed during the Visit 13 in-person evaluation:

[figure not shown]
- Inspection of lead exit site
- Diagram of pain [REDACTED]
- ROM [REDACTED] and pain during ROM
- Six-Minute Walk Test
- TUG Test

- WOMAC
- PCS

In addition, subjects will be queried for adverse events. If no AEs are noted, the subject will be discharged from the study following the 3-month visit. Any AE will be documented, addressed, and followed to resolution.

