8.1 Analysis of Outcomes and Exploratory Measures

A table of outcomes and exploratory measures to be collected during the study can be found in Appendix A.

Question 5 of the Brief Pain Inventory-Short Form (BPI-5) is an 11-point numerical rating scale rating “Average Pain”. The BPI-5 will be measured at Visit 1 to establish a baseline score, as well as daily during stimulation and monthly post-EOT. For each subject, the mean over the first 4 weeks following TKA surgery will be calculated. An overall mean across all subjects for the first 4 weeks following TKA surgery will be calculated as well. This outcome will also be compared to historical controls (e.g., published data).

Additionally, sub-analyses will be performed to determine the mean over different post-operative phases (such as acute (e.g., days 1-7) or subacute (e.g., days 7-28)); calculate the mean for each subject and across subjects up to End of Treatment (week 6); and evaluate the proportion of subjects with pain below a certain threshold (e.g., 4/10).

Subjects will also rank their daily “Average Pain” (BPI-5) while walking. These data will undergo the same analysis as listed above for the standard BPI-5. This outcome will also be compared to historical controls (e.g., published data).

At the weekly visits during stimulation, subjects will be asked to report their weekly “Average Pain” (BPI-5) while at rest. The mean over different intervals (such as weeks 1-4 or weeks 1-6) will be calculated.

At each study visit, pain treatments and analgesic usage will be recorded. Changes in analgesic usage will be calculated using morphine equivalent dosing (MED). The usage of analgesics over various intervals (such as weekly averages, during weeks 1-4, etc.) will be calculated.

Medication usage will also be compared to pain scores to examine the correlation between analgesic usage and pain. The time to cessation of opioid will be determined. Also at each study visit, subjects will be queried for opioid related side effects. The number of effects noted over various intervals will be calculated.

Range of motion [REDACTED] will be collected at visits before, during, and after treatment. The time to achieve milestones (e.g., 90 degrees flexion, 100 degrees flexion) will be calculated for each subject and across all subjects. The mean flexion, extension, and range of motion (flexion – extension) across all subjects will be determined. The same will be calculated for passive ROM and active ROM.

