Functional tests performed during the study will include the Timed Up and Go (TUG) test, the Six-Minute Walk Test, and the Fixed Distance Walk Test. The TUG test will be analyzed to determine the mean time across subjects at each time point. The 6MWT will be used to calculate the mean distance across subjects at each time point. Data from the Fixed Distance Walk Test will be used to compute the mean time across subjects at each time point.

Surveys performed during the study will include the Western Ontario and McMaster Universities Arthritis Index (WOMAC), Pain Interference (as measured by question #9 of the Brief Pain Inventory), Patient Global Impression of Change (PGIC), time to meet recovery milestones, Subject Satisfaction Survey, and Clinician Satisfaction Survey. The WOMAC will be used to calculate a mean total score across all subjects, means score of specific subsections or individual questions, and to calculate differences in scores post-operatively compared to pre-operatively. BPI-9 will be used to calculate differences in scores post-operatively compared to pre-operatively for individual subjects as well as across all subjects. A mean PGIC score will be calculated across all subjects. The time to meet recovery milestones will be used to compute the mean number of days to achieve each milestone. Frequency of answers will be determined for specific questions of the Subject Satisfaction Survey and Clinician Satisfaction Survey.

Throughout the study, subjects will complete self-shaded diagrams of areas of pain

The mean and standard deviation of the percent overlap will be calculated across subjects.

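### Recovery milestones are summarised as a plain mean number of days, with no rule for subjects who have not reached the milestone when follow-up ends at 3 months (minor).

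*Combined protocol and SAP*

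**What the plan says.** Section 8.1 sets the summary for recovery milestones: "The time to meet recovery milestones will be used to compute the mean number of days to achieve each milestone". The same section says of opioids: "The time to cessation of opioid will be determined". That sentence names no estimator.

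Section 3.3 says that, beyond discharge criteria and length of stay, "the time required to reach other important recovery milestones may be measured". Its list covers walking with and without an assistive device, "3) return to work, and 4) cessation of narcotic usage". The Synopsis lists time to recovery milestones as a secondary endpoint and gives the discharge date as its example.

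On follow-up, section 6.5.8 says that, if no adverse event is noted, "the subject will be discharged from the study following the 3-month visit". On dating, section 3.3 says analgesic use is taken from hospital records during the stay, then "in daily diaries after discharge from the hospital, and at each visit following End of Treatment". Separately, sections 6.5.5 to 6.5.8 list time to recovery milestones among the measures that may be assessed in hospital and at Visits 6 to 13.

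The only missing-data rule is in section 8.2. It replaces unreturned pain diaries with one-week recall and restricts imputation to scores. The protocol does not mention censoring, a survival estimate, a restricted mean, an assigned value, or reporting how many subjects reached a milestone. The visible redactions in 8.1 do not touch the milestone or opioid sentences.

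**The concern.** A subject still taking opioids, or not back at work, at the 3-month visit has no number of days to enter into a mean. The analyst must drop that subject, enter a value such as day 90, or treat the time as censored. These choices give different answers from the same data, and the plan does not choose.

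Dropping non-achievers gives a mean that describes only those who recovered within the window, and without the number achieving a reader cannot see this. Section 3.3 says of the secondary outcomes: "which will be used to aid in the design of future clinical studies". If a sizeable share do not achieve, later studies could inherit times that are too short.

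**Working it through.** **Inputs.** The documents give up to 36 subjects (section 5.2) and follow-up to 3 months, taken here as T = 90 days. They give no milestone rate and no planned figure to reproduce. The Background's figure of up to 27% without full functional recovery at 1 year or later is not a rate for any milestone at 3 months, so it is not used. The share not achieving, S, and the shape of the time distribution are assumptions.

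**Identity (no distribution needed).** Let A be the achievers' mean and R the mean restricted to 90 days. With everyone followed to day 90 and exact dates, R = (1 − S)·A + 90·S, so R − A = S·(90 − A). Example: if 29 of 36 achieve with a mean of 40 days (assumed) and 7 do not, R = (29 × 40 + 7 × 90)/36 = 1790/36 = 49.7 days, against 40.

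**Exponential times.** Rate λ = −ln(S)/90, R = (1 − S)/λ, A = (R − 90·S)/(1 − S). At S = 0.20: λ = 1.609/90 = 0.01788; R = 0.80/0.01788 = 44.7; A = (44.7 − 18)/0.80 = 33.4; gap = 0.20 × (90 − 33.4) = 11.3.

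**Sampling error of A.** The 95% half-width is 1.96·SD/√(36·(1 − S)). At S = 0.20: 1.96 × 24.4/√28.8 = 8.9.

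**Visit-dated opioid cessation.** Suppose dates are exact to day 42 and a later stop is dated to an assumed day 61 or day 90. At S = 0.20 the chance of stopping in days 42–61 is 0.136, and in days 61–90 also 0.136. Stops up to day 42 contribute 9.7. The visit-dated achievers' mean is V = (9.7 + 61 × 0.136 + 90 × 0.136)/0.80 = 37.8, so V − R = 37.8 − 44.7 = −6.9.

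| S | A | R | R − A | SD of A | half-width of A | V − R |
|---|---|---|---|---|---|---|
| 2% | 21.2 | 22.5 | 1.4 | 19.0 | 6.3 | +0.5 |
| 10% | 29.1 | 35.2 | 6.1 | 23.0 | 7.9 | −2.6 |
| 20% | 33.4 | 44.7 | 11.3 | 24.4 | 8.9 | −6.9 |
| 30% | 36.2 | 52.3 | 16.1 | 25.1 | 9.8 | −11.2 |

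**Crossing points, solved numerically.** With exact dates the gap equals the half-width at S of about 14%. With visit dating the shortfall reaches the same half-width at about 26%, and the sign changes near 4%. Visit-dated times are also more spread out: at S = 30% their SD is 30.8, giving 1.96 × 30.8/√25.2 = 12.0, which is more than 11.2. Against that wider half-width the crossing moves to about 33%.

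**Other shapes, exact dates.** Weibull with shape 1.5 or 2 and log-normal with log-SD 0.5 or 0.8 give gaps of 4.3 to 5.6 days at 10% and 9.9 to 13.3 at 30%.

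**How likely is a non-achiever?** At S = 5%, the chance of at least one among 36 is 1 − 0.95³⁶ = 0.84.

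**The case against.** The case against has four parts, and most of it stands as a limit on the point.

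First, a reader might infer that the plan commits to a mean over achievers, and does so for opioid cessation. It does not. Section 8.1 says only that the opioid time will be determined. The mean reaches opioid cessation through the section 3.3 milestone list, whose items only may be measured. An achievers-only mean is the likely default, not a stated rule. The plan still does not say how non-achievers are counted.

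Second, a reader might infer that only status is recorded at each visit, so that dates are lost. The documents do not support this. Time to recovery milestones is itself a listed measure at Visits 6 to 13. The case report forms are not among the documents, so the visit-dated row is a scenario and not a description of the study. The visit windows are also blank, so days 61 and 90 are assumed.

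Third, a reader might infer that the reported times will certainly be too short. Size depends on unknown shares, and under visit dating so does direction. At low shares sampling error exceeds the gap. Percentages measured against a mean extrapolated beyond day 90 would look larger, but they concern a quantity this study cannot observe. For flexion milestones, which are also timed in 8.1, dates depend on when range of motion is measured, so no direction is claimed.

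Fourth, the restricted mean's own half-width at 10% not achieving (9.3 days) exceeds the 6.1-day gap that it corrects. This is true, but the achievers' mean is nearly as imprecise (7.9 days). A confidence interval shows sampling error; it does not show an unstated exclusion.

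**Conclusion.** The point holds in a limited form. The stated summary is undefined for subjects who have not reached a milestone by 3 months, and no rule fills the gap. With exact dates, full follow-up and exponential times, an achievers' mean would be about 1 to 16 days below the 90-day restricted mean as the assumed share not achieving goes from 2% to 30%. If late opioid stops are dated only to the visit, the difference runs from +0.5 to −11.2 days. It matters beyond sampling error only above about 14% not achieving in the first case and at least about 26% in the second. None of these shares comes from the documents.

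For milestones nearly everyone reaches, such as discharge, the effect is negligible. These are descriptive secondary outcomes of an uncontrolled feasibility series. The primary pain endpoint is unaffected, and nothing here suggests that it is at risk. This is a minor point that is cheap to settle before analysis.

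**What to change.** In section 8.1, for opioid cessation, and for walking and return-to-work milestones where they are measured:

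- Report the number and percentage achieving by 3 months.
- Replace the plain mean with a Kaplan-Meier median, or a mean restricted to 3 months, with a 95% confidence interval, censoring non-achievers at last contact. Censoring also deals with subjects who withdraw early.
- Define who is counted: opioid cessation among those who used opioids after surgery, and return to work among those working before surgery.
- Use the milestone times already listed for collection at Visits 6 to 13.

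Discharge and length of stay can keep a simple mean with n shown.

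The cost is analysis-plan wording and standard code. Return to work needs work status before surgery; whether this is already recorded cannot be seen from the documents. Reported times become somewhat longer for milestones that many subjects miss. The median is undefined if fewer than half achieve. The restricted mean remains imprecise: with an SD of 28.4 to 32.4 days at 10% to 30% not achieving, 1.96·SD/√36 is 9.3 to 10.6 days, so roughly 9 to 11.

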8.2 Plan to maximize subject retention and minimize loss of data

Significant efforts will be made to maintain maximum subject retention and follow up data and minimize the percentage of missing data.

A potential source of data loss is the failure of the subjects to return their completed diaries. Thus, subjects may receive reminder calls from the clinical study staff before certain visits to remind them to bring their completed diaries with them to the visit.

Subject withdrawal from the study is a potential source of data loss. Study investigators and staff will be trained to have clear discussions with subjects considering withdrawing from the study.

Subjects are offered compensation for each visit as it is completed, including unscheduled visits, even if they do not complete all the visits. This compensation is intended to cover costs associated with taking the time to participate in the study. Sites are also provided with a travel budget for which they are able to reimburse subjects for the actual incurred mileage or mobility transportation arrangements can be provided.

If a subject is unable to return any follow-up diary, the data will be replaced using the one-week recall data (question #5 of the validated BPI-SF). The question may be collected verbally over the phone if needed. This method will mitigate the problem of missing data and minimize the need to impute scores. Scores will only be imputed if recall data are unavailable and cannot be obtained. If the subject later returns the diary, the diary data will be used over the one-week recall data.

Additional steps will be taken as necessary to maintain a high level of subject participation and follow up. For example, if a subject relocates during the study, arrangements will be made either to provide transportation for the subject to attend their visits at the clinical site, or to allow the subject to receive the necessary follow up at a medical center in closer proximity to their new location and a referring physician located near the subject will conduct the visit with the assistance of an investigator and/or a technical representative from SPR Therapeutics as needed.

8.3 Safety Endpoint Analysis

All adverse events will be documented, reported, and categorized so that the safety profile of this approach may be further understood. Knowledge gained from this study will further refine consent forms and the risk benefit profile for future studies.

9.0 STUDY MONITORING

9.1 Training

SPR Therapeutics or their designee will conduct a Site Initiation and Training Visit prior to initiation of the study. The purpose of this visit will be to develop a common understanding of the clinical protocol, Case Report Forms (CRFs), study specific procedures, Investigator Responsibilities, and Good Clinical Practices (GCPs) among the clinical research monitors and the Investigational Site team.

9.2 Routine Monitoring

Monitoring visits to the Investigational Site will be conducted periodically, as determined by the rate of subject enrollment, during the study to ensure that the most currently approved version of the Investigational Plan is being followed and that the site is in adherence with all Good Clinical Practices and any specific study Data Monitoring Plan that is in place. In addition, source documents will be reviewed for accuracy against data found on the Case Report Forms.

[REDACTED]

[REDACTED]

9.3 Device Accountability

Device accountability will be maintained by the Investigational Site.

[REDACTED]

9.3.1 Returning used devices to SPR Therapeutics

The site will record any devices returned to SPR Therapeutics in the Device Accountability Log. The site will contact SPR to obtain a Return Goods Authorization (RGA) number prior to returning any devices.

10.0 ADVERSE EVENTS AND UNANTICIPATED ADVERSE DEVICE EFFECTS

Adverse events (AEs) that occur during the study will be captured on CRFs. Specific details regarding any observed AE will be collected on a separate Adverse Event Form. The severity of each Adverse Event will be collected as well as its relationship to the System. AEs will be classified as mild (event that causes mild discomfort or inconvenience and resolves without treatment), moderate (event that requires medical intervention or medication to treat), or severe (event that requires intervention to prevent permanent impairment or damage, an event that requires or prolongs hospitalization, or an event that is disabling, causing permanent damage, life threatening, or causing death). Adverse events will also be classified as serious or non-serious. Any necessary treatment or intervention required and the resolution status of the adverse event will also be documented. Adverse Events will be followed to resolution. Side effects from narcotic therapy will be collected but not reported as adverse events.

An Adverse Device Effect (ADE) is a device-related Adverse Event. All ADE's are further categorized as anticipated or unanticipated. Any ADE's specified in the Risk Analysis of this Investigational Plan will be considered "anticipated". All other ADE's are considered "unanticipated". Anticipated events that occur with a greater frequency than expected are also considered unanticipated.

An Unanticipated Adverse Device Effect (UADE) is defined as any serious adverse effect on health or safety or any life threatening problem or death caused by, or associated with, a device, if that effect, problem or death was not previously identified in nature, severity or degree of incidence in this Investigational Plan or application or any other unanticipated serious problem associated with a device that relates to the rights, safety or welfare of subjects.

UNANTICIPATED ADVERSE DEVICE EVENT SPONSOR CONTACT INFORMATION			
Name/Title	Email address	Telephone Number	Fax Number
[REDACTED]	[REDACTED]	[REDACTED]	[REDACTED]
[REDACTED]	[REDACTED]	[REDACTED]	[REDACTED]
[REDACTED]	[REDACTED]	[REDACTED]	[REDACTED]

Table 2 Unanticipated Adverse Device Event Sponsor Contact Information

UNANTICIPATED ADVERSE DEVICE EVENT SPONSOR CONTACT INFORMATION			
Name/Title	Email address	Telephone Number	Fax Number
[REDACTED]	[REDACTED]	[REDACTED]	[REDACTED]
[REDACTED]	[REDACTED]	[REDACTED]	[REDACTED]
[REDACTED]	[REDACTED]	[REDACTED]	[REDACTED]

It is the responsibility of the investigator to inform his/her Institutional Review Board (IRB) of any ADEs and UADEs as required by the IRB. In addition, some IRBs will require that AEs that are serious in nature, even if not device related, will be reported as well. SPR Therapeutics is responsible for furnishing the required information to the appropriate regulatory authorities.

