3.5 Safety Endpoint

The primary safety endpoint is the occurrence of device related adverse events. All adverse events (AEs) that occur during the study will be documented. Specific details regarding any observed AE will be collected on an Adverse Event Form and will be followed to resolution. Adverse Events will be tabulated and summarized at the conclusion of the study.

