11.2 Known and Anticipated Risks

The risks listed below are described as common ([REDACTED]), uncommon ([REDACTED]), or rare ([REDACTED]).

1) Risks associated with insertion of the needle introducer for lead placement

2) Risk of nerve damage from the needle or lead.

[figure not shown]

3) Risk of skin irritation, infection, or inflammation at the lead exit site

[figure not shown]
[REDACTED]

4) Risk of the percutaneous lead breaking beneath the skin

[REDACTED]

[figure not shown]
5) Risks associated with retained Percutaneous Lead fragments

A large rectangular area of the page has been completely blacked out, indicating that the content has been redacted.

6) Risks associated with lead fragment removal

[figure not shown]
7) Risk of lead replacement

[figure not shown]
8) Risk of skin irritation under the Sprint pad, Smartpatch lead connector tape, bandages, or belt

[figure not shown]
9) Risk of mechanical or electrical failure of the Sprint stimulator

10) Risks for pregnant women

11) Risk of discomfort or increased pain

12) Risk of worsening of pain symptoms

13) Risk of tissue damage

14) Risk of falls

15) Risks associated with Diathermy

16) Risks associated with MRI

17) Risk of allergic reaction to local anesthetics (if applicable)

18) Risk associated with venipuncture (if applicable)

19) Risk associated with conscious sedation (if applicable)

20) Risk of loss of confidentiality

21) Risk of swallowing or choking on battery

[figure not shown]

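### Side effects attributed to narcotics are exempt from adverse-event reporting with no exception for severe or serious events, so such events reach the data only as a count

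*Combined protocol and SAP*

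**What the plan says.** Section 3.5 sets the general rule: "All adverse events (AEs) that occur during the study will be documented". It makes device-related adverse events the primary safety endpoint and calls for all events to be followed to resolution and tabulated.

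Sections 3.3 and 10.0 then carve out one class of event, in the same words: "Side effects from narcotic therapy will be collected but not reported as adverse events". Section 3.3 names what that class typically contains: "Common side effects include nausea and vomiting, constipation, urinary retention, pruritis, drowsiness, and respiratory depression".

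The exempt effects are handled as a pain-related secondary endpoint. Section 8.1 says "Also at each study visit, subjects will be queried for opioid related side effects", and gives the analysis in one sentence: "The number of effects noted over various intervals will be calculated".

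Section 10.0 specifies, for adverse events, a mild, moderate or severe grade, a serious or non-serious class, the relationship to the System, treatment given, resolution status and follow-up. Its top grade covers events that lengthen a hospital stay, threaten life or cause death. On ethics-board reporting it notes that "some IRBs will require that AEs that are serious in nature, even if not device related, will be reported as well".

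**The concern.** Routine opioid nausea or constipation after knee replacement would swamp an adverse-event listing, and keeping it apart is sensible. But the exemption is drawn by presumed cause alone, not by cause and gravity. Two of the listed effects, respiratory depression and urinary retention, can be grave enough to lengthen a stay, and the first can threaten life. Under the rule as written, such an event never becomes an adverse event once it is attributed to a narcotic.

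Two things are at stake. The first is the overall safety profile. Section 1.5 makes safety part of the objective, and Section 8.3 says the findings will refine consent forms and the risk-benefit profile of later studies. The second is attribution. The judgment that an event comes from narcotics precedes, and removes, the step at which its relationship to the System would be recorded.

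**Working it through.** The point involves no stated figure, so the check sets the provisions side by side and follows an event through them.

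**1. What each kind of event receives**

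| Step | Adverse event | Effect attributed to a narcotic |
|---|---|---|
| Collected | Yes (3.5, 10.0) | Yes (3.3, 8.1) |
| Severity grade | Yes (10.0) | None specified |
| Serious / non-serious class | Yes (10.0) | None specified |
| Relationship to the System | Yes (10.0) | None specified |
| Resolution status and follow-up | Yes (3.5, 10.0) | None specified |
| Ethics-board report if serious but not device related | Where the board requires it (10.0) | Not reached: the sentence speaks of AEs |
| Analysis | Tabulated and categorized (3.5, 8.3) | Number of effects per interval (8.1) |

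**2. Is there an exception for grave events?** The exemption sentence appears twice, in 3.3 and 10.0, with no limit by severity, seriousness or outcome. The other readable text on adverse events, opioid side effects, visits, safety analysis and risks (3.1, 3.5, 6.5, 8.1, 8.3, 10.0, 11.2, Appendix A) supplies none.

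**3. Three events followed through the rule**

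- *Itching from an opioid.* Exempt and counted as one effect. Little is lost.
- *Life-threatening respiratory depression attributed to an opioid.* As an adverse event it would be graded severe under 10.0. It is exempt, so it is ungraded and counted as one effect, on a par with the itching.
- *Marked drowsiness around lead placement, cause unclear.* Whether it reaches the Adverse Event Form depends on a first judgment of cause. The readable text does not say who makes that judgment or by what standard. Section 6.5.4 allows consent, lead placement and surgery on one day, so possible causes can coincide.

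**4. Effect on the primary safety endpoint.** The endpoint counts device-related adverse events.

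- A true narcotic effect contributes 0 whether exempt or not.
- A device-related event attributed correctly contributes 1.
- A device-related event attributed to a narcotic contributes 0 instead of 1, with no relationship rating on record.

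Only the third case changes the endpoint.

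**5. Does the unanticipated-device-effect route close the gap?** The definition in 10.0 has no narcotic carve-out, but it requires a serious event caused by or associated with the device. An event already put down to an opioid has, by that judgment, no device link.

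**The case against.** The strongest case on the other side is that this is a coherent definition. A general rule with a specific exemption, stated identically in two places, is not a contradiction. Expected effects of permitted analgesics get their own outcome, their own schedule row and a place in most of the visit lists. The exemption covers only effects of narcotic therapy, so on its plain wording an event from the device, lead placement or another sedative remains an adverse event. Section 6.5.3 adds a call 24 to 48 hours after lead placement to ask about adverse events, except where 6.5.4 waives it for same-day surgery. Section 3.3 records length of stay for every subject.

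Much of this stands. Sections 3.5 and 10.0 do not contradict each other, and separating routine opioid effects is reasonable. What it does not answer is the lack of any limit by gravity: length of stay and a count of effects do not replace a severity grade, a seriousness class and follow-up.

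Three stronger readings are tempting, and the documents do not support them.

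- *The events vanish from the study.* They do not; they leave the adverse-event record and its analysis only. Section 3.3 does say "Subjects may be questioned for each of these side effects throughout the study", but Section 8.1 has the firm wording on querying at each visit, so the permissive phrase cannot carry an argument that collection is optional. The two should simply be aligned.
- *The primary safety endpoint is biased downward.* That needs misattribution, and nothing in the documents shows that it will occur or how often.
- *Procedural sedation will be miscoded as a narcotic effect.* Section 11.2 lists conscious sedation as a risk where applicable, but only the heading is readable. The agents used and any attribution instructions are unknown, so this is a possibility and no more.

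**Conclusion.** The concern holds as a gap in the reporting rule. Read as written, Sections 3.3 and 10.0 leave even a life-threatening event attributed to an opioid outside the adverse-event record, and so outside grading, seriousness classification, relationship rating, required follow-up and the safety analysis. The loss to the overall safety profile is direct. The effect on the primary safety endpoint is conditional on misattribution.

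No number can be put on it. The documents give no rate of serious opioid effects and no rate of misattribution. A reader might assume a rate and work out the chance of at least one serious opioid event among 36 subjects. That would describe how often such events occur, not how far the device-related count is distorted.

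The conclusion rests on the exemption sentences, which are readable in full, and on the absence of an exception elsewhere in the readable text. The absence of an attribution rule is less certain, because much of Section 11.2 is redacted.

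**What to change.** In both Sections 3.3 and 10.0, limit the exemption to effects that meet all three conditions:

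1. they do not meet the definition of severe in Section 10.0;
2. they are not classified as serious;
3. the investigator judges them clearly due to a narcotic.

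Record any other such effect on the Adverse Event Form with its relationship to the System rated. This includes an effect that could plausibly come from the device, lead placement or its sedation. State that severity and seriousness are assessed before the exemption is applied; otherwise the second condition has nothing to act on. The readable text defines severe but not serious, so a definition of serious should be added or cited alongside.

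Keep the full side-effect count in Section 8.1 as the secondary outcome, so nothing is lost there, and note in the tables that some effects appear in both places. Align the wording on querying in Sections 3.3 and 8.1.

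The cost is one revised sentence in each of two sections, a few extra forms and a slightly higher adverse-event count. The change concerns reporting only and leaves clinical management untouched.
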